6 RESEARCH QUESTION AND OBJECTIVES

6.1 Research Question

The aim of this registry-based study is to collect real-world safety data and to describe the effectiveness of chronic odevixibat treatment in participants with ALGS.

6.2 Objectives

6.2.1 Primary Objective

To evaluate the incidence of biliary diversion surgery, liver transplantation, all-cause mortality in participants with ALGS chronically treated with odevixibat.

6.2.2 Secondary Objectives

- To evaluate the growth and development of participants with ALGS treated with odevixibat.
- To evaluate the incidence of FSV deficiencies and their possible sequelae in participants with ALGS treated with odevixibat.
- To evaluate the incidence of suspected hepatotoxicity requiring interruption of odevixibat treatment.
- To evaluate the incidence of bleeding events in participants with ALGS treated with odevixibat.
- To assess real-world safety data of odevixibat in participants with ALGS.

PAGE 22 OF 76

7 RESEARCH METHODS

7.1 Study Design

This will be a long-term, observational, prospective, and voluntary participation registry-based study designed to collect and assess real-world data on participants with ALGS chronically treated with odevixibat.

The study population will comprise participants with ALGS treated with odevixibat enrolled into the registry-based study. Participants who started odevixibat treatment before the implementation of the registry-based study may also be enrolled.

As this is an observational study designed to assess real-world data, the decision to prescribe the product must be taken prior to, and independently from, the willingness of the participant to be included in the registry-based study. This decision should be made in accordance with routine/standard clinical practice. The assignment of the participant to a particular therapeutic strategy is not decided in advance by the study protocol but falls within current practice.

Participants will be treated and monitored in accordance with usual medical practice during their participation in this registry-based study. No additional assessments or tests will be required by this protocol. All relevant data collected as part of routine medical care will be captured using the electronic Case Report Form (eCRF) by the investigator and transmitted to the sponsor. If some assessments included in this protocol are not routinely performed by the investigator, the corresponding sections in the eCRF do not need to be completed.

This registry-based study will collect data at Baseline and at each Follow-up Visit. Follow-up Visits are scheduled as per routine clinical practice (expected to occur at least every 6 months or more frequently, based on the investigator's judgement).

The duration of this registry-based study is approximately 5 years. Following enrolment, participants will continue to participate in the study for ≥ 2 years or until the time point of withdrawal of consent, for up to 180 days after last dose of odevixibat (in case of treatment discontinuation), death, the end of data collection, or the sponsor decides to discontinue the study.

The primary objective of this registry-based study is to evaluate the incidence of biliary diversion surgery, liver transplantation, and all-cause mortality in participants with ALGS chronically treated with odevixibat. The secondary objectives are to evaluate the growth and development, incidence of FSV deficiencies and their possible sequelae, evaluate the incidence of suspected hepatotoxicity requiring interruption of odevixibat treatment and bleeding events (including events requiring emergency department care, hospitalization, or blood transfusion) and assess real-world safety data of odevixibat in participants with ALGS.

7.2 Setting

7.2.1 Inclusion Criteria

To be included in the registry-based study, the participant should fulfil the following inclusion criteria:

- (1) Diagnosed with ALGS.
- (2) On (or starting) active odevixibat treatment.
- (3) Signed informed consent and assent, as appropriate. Consent/assent from the participant or legal representative should be obtained, as appropriate, before any study data collection is conducted. Participants who turn 18 years of age (or legal age per country) while participating in the study will be required to provide consent for themselves.

PAGE 23 OF 76

7.2.2 Exclusion Criteria

Participants will not be included in the registry-based study if:

- (1) Currently participating in a clinical trial with odevixibat.
- (2) Currently participating in any interventional clinical trial for ALGS.
- (3) Have any contraindication to odevixibat as per the locally approved label.
- (4) Had liver transplant before enrolment.

Individuals who do not meet the criteria for participation in this registry-based study (screen failure) or who withdraw their consent may be rescreened. Rescreened participants should be assigned a new participant number. The informed consent process is described in Section 7.13.

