7.2.8 Study Discontinuation/Withdrawal

The participant can withdraw (or be withdrawn if the participant is a child upon legal representative's decision) from this registry-based study at any time. The date and primary reason for withdrawal should be recorded in the eCRF as well as if the participant stopped odevixibat or not.

For study results to remain unbiased, it is important that no data are modified; as a result, the data collected in clinical studies need to remain untouched for results to be trusted. Should the participant withdraw from the study, no further data will be collected; nevertheless, data collected up to the time of the withdrawal will be kept for analysis, safety, and integrity of study results.

PAGE 28 OF 76

The participant will be withdrawn from the registry-based study if:

- They enroll in any interventional clinical trial
- The participant is no longer receiving odevixibat and has completed the last follow-up visit up to 180 days after last dose of odevixibat (see Section 9.4 for follow-up of AEs and Section 9.1.3.1 for follow-up of pregnancies)

Note: Participants can remain in the registry-based study during odevixibat treatment interruptions.

Investigators may decide to stop their participant's participation in the study at any time without consequences on the normal participant follow-up.

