7.6.1 Data Collection

The specific data to be collected at each visit, if available, are summarized in the schedule of assessments (Table 1).

All relevant data collected as part of routine medical care will be captured using the eCRF by the investigator and transmitted to the sponsor. If some assessments included in the protocol are not routinely performed by the investigator, the corresponding sections in the eCRF do not need to be completed.

Data will be collected in an eCRF via the internet utilizing a secured website. The sponsor and the SP will ensure that the eCRF developed is appropriate to capture the data required by the protocol. The sponsor will ensure that the entrusted SP uses adequate technology to ensure data security transfer and backup.

Each site is required to have a computer and internet connection available for site entry of clinical data. Data entry in the eCRF will be performed by the investigator or by the designated person from their team and to ensure confidentiality and security of the data, all entries into the eCRF will be made under the electronic signature (e-signature) of the person performing the action (username and password). Only sponsor-authorized users will be given access to the eCRF as appropriate for their study responsibilities. All users must have successfully undergone software application training prior to entering data into the eCRF.

Once the signed informed consent (and assent, if applicable) has been obtained, the eCRF will provide a numeric participant identifier to pseudonymize the data from each participant. Data for each participant must be entered into the eCRF within 5 days of the participant's enrolment and each Follow-Up Visit. Data transmitted will be pseudonymized and will be identified only by the participant number. Only investigating sites will be able to link the numeric identifier to each participant's identity.

PAGE 32 OF 76

In compliance with Good Pharmacoepidemiology Practices (GPP), the participant's medical records should be clearly marked and permit easy identification of their participation in this registry-based study.

Medical and surgical history, concomitant surgeries, Special Situations, and AE terms will be coded using the Medical Dictionary for Regulatory Activities (MedDRA) and prior/concomitant medication and vitamin supplementation will be coded using the World Health Organization Drug Dictionary by the contracted SP and reviewed by the sponsor.

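### A participant who withdraws consent and returns gets a new number with no required link to the old one, so one person can enter the analysis twice

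*Protocol*

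**What the plan says.** Five parts of the protocol bear on this.

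- **Section 7.2.2 (Exclusion Criteria).** Two groups may come back: people who fail the entry criteria, "or who withdraw their consent may be rescreened". For both, "Rescreened participants should be assigned a new participant number".
- **Section 7.2.8 (Study Discontinuation/Withdrawal).** After withdrawal collection stops, but "data collected up to the time of the withdrawal will be kept for analysis, safety, and integrity of study results".
- **Section 7.6.1 (Data Collection).** "Data transmitted will be pseudonymized and will be identified only by the participant number". It adds: "Only investigating sites will be able to link the numeric identifier to each participant's identity".
- **Section 8.1.** The sponsor gives each participant a unique identification number at enrolment.
- **Section 7.7.1.** The Safety Population is everyone who takes at least one odevixibat dose after enrolment. It has no provision for a person enrolled twice.

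The protocol nowhere asks the site to record the earlier number when a returning participant is given a new one.

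**The concern.** A new number after screen failure does no harm, because a screen failure leaves no analysed record. The difficulty is that the same rule covers someone who was enrolled, took odevixibat in the registry, withdrew, and later re-consented. That person's first record stays in the analysis, and the second arrives under a different number. Each meets the Safety Population definition.

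The primary time-to-event endpoints in Section 7.3.1.1 all run from the start of odevixibat, and Section 7.1 admits people already on treatment. If the original start date is entered on both records, they share a time origin, and the first months on drug are counted once in each. The second record also belongs to someone who is necessarily alive and, under exclusion criterion 4, transplant-free at re-entry. Unless delayed entry is applied, its time before re-entry can contain neither event.

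At stake are the denominators for incidence and adverse events, the baseline summaries, the risk sets in the Kaplan-Meier curves, and the independence of the observations. The annual interim analyses in Section 7.7.4 would carry the same duplicate forward.

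**Working it through.** The protocol gives no sample size calculation and no expected number of re-entries, so there is no stated figure to reproduce. What follows shows the size under stated assumptions.

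**Inputs.** The enrolment goal is N = 30 to 45 (Section 7.5). The number of duplicate records, k, is assumed to be 1 to 3. For illustrative event counts I use the 15% to 25% childhood transplant figure in Section 5.2; it is background, not a planning assumption.

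**Denominator.** Inflation is k/N. With k = 1: 1/45 = 2.2% and 1/30 = 3.3%.

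**Crude incidence, each event recorded once.** The true value is x/N and the reported value x/(N+k), a relative change of N/(N+k) − 1.

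- N = 30: k = 1, 2, 3 gives −3.2%, −6.2%, −9.1%. With 8 events, 8/30 = 26.7% becomes 25.8%, 25.0%, 24.2%.
- N = 45: −2.2%, −4.3%, −6.2%. With 11 events, 11/45 = 24.4% becomes 23.9%, 23.4%, 22.9%.
- With 3 events in 30 and k = 2, 3/30 = 10.0% becomes 3/32 = 9.4%.

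**Crude incidence, one event recorded under both numbers.** The reported value is (x+1)/(N+1).

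- N = 30: 4/30 = 13.3% becomes 5/31 = 16.1% (+2.8 points); 8/30 = 26.7% becomes 9/31 = 29.0% (+2.4 points).
- N = 45: 7/45 becomes 8/46 (+1.8 points); 11/45 becomes 12/46 (+1.6 points).

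This could happen with biliary diversion. A diversion before withdrawal would be an event on the first record and prior surgery at the second baseline (Section 7.2.7.1).

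**Kaplan-Meier at 36 months, constructed data.** N = 30 people: 6 events at months 3, 9, 15, 21, 27 and 33; 23 event-free to month 36; one person out at month 12 and back at month 18.

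- One linked record, gap unobserved. The numbers at risk are 30, 29, 27, 27, 26, 25. Survival = (29/30)(28/29)(26/27)(26/27)(25/26)(24/25) = 0.799.
- Two records from treatment start, no delayed entry. The numbers at risk are 31, 30, 28, 27, 26, 25. Survival = (30/31)(29/30)(27/28)(26/27)(25/26)(24/25) = 0.802.

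The difference is about 0.003. The same construction with N = 45 and 9 events gives 0.799 against 0.801.

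**Scale.** The exact 95% interval for 8/30 is 12.3% to 45.9%, so a single duplicate moves the estimate by far less than its sampling uncertainty.

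**The case against.** A reader might infer that the sponsor is unable to link the two records, or that one person will necessarily be analysed as two. The protocol supports neither. Section 7.6.1 restricts linking a number to an identity; it does not bar linking one number to another. The site holds the key and could report the old number without disclosing who the person is. Monitors see source documents and verify consent, eligibility and the primary variables (Section 7.8.1), and sponsor-authorised staff may view medical records (Section 7.8.3). The sponsor also receives sex, month and year of birth, genetic variant, diagnosis date and odevixibat start date where available. Among 30 to 45 people with a rare disease, a matching pair could well be noticed. All this stands. It makes detection possible, but nobody is instructed to look.

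It can be said that counting persons belongs in the SAP, which Section 7.7.2 makes a separate document. That is fair for the analysis rule. But the numbering and the data captured are fixed in the protocol, and a SAP cannot reliably merge records without a captured link.

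Section 7.2.2 might also be meant only for people who withdraw around screening, and Section 7.2.8 says nothing about re-entry. The wording is not limited in that way, so the intention needs stating.

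Three further limits stand:

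- The bias is not always towards fewer events, as the diversion example shows.
- First-period adverse events would not routinely be collected again, because collection starts at consent (Section 9.2.1). The likelier effect is on the adverse event denominator, with duplication possible for events still ongoing.
- Unobserved time between treatment start and enrolment affects every participant already on odevixibat. Renumbering does not cause it; it only adds a second copy.

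**Conclusion.** The point holds as an unguarded risk created by the stated rules: a new number after withdrawal of consent, retained earlier data, data identified only by number, and no required cross-reference. Section 8.1's unique number per participant does not fit a second number for the same person.

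The size is small. One re-entry inflates the denominator by 2.2% (N=45) to 3.3% (N=30) and shifts 36-month survival by about 0.002 to 0.003 in the constructed data. The usual direction is slightly optimistic, because the second record starts alive and transplant-free; a double-counted diversion would work the other way. These figures assume one re-entry, the original odevixibat start date on both records, and no delayed entry. Only people who re-enrol before enrolment closes at 3 years (Section 7.2.4) can contribute. The analyses are descriptive, with no formal testing (Section 7.9), so no test result is at risk. The change is worth making because the rule is plainly loose and nearly free to correct, not because the bias is large.

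**What to change.** 1. In Section 7.2.2, either limit the new participant number to screen failures, so that a participant who re-consents keeps the original number, or require the site to enter the previous number in the eCRF at re-consent. Either works, provided the link is captured.
2. Reconcile Section 8.1 with whichever rule is chosen.
3. State that analyses use one record per person, with the two periods joined, the time between withdrawal and re-consent treated as unobserved, and the person returning to the risk set at re-consent.

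The protocol cost is one sentence in Section 7.2.2, with wording aligned in Section 8.1, and one eCRF field. It is best done before any re-entry occurs.

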7.2.3 Study Population

Eligible participants will be participants with ALGS who have been prescribed odevixibat by their treating physician. To be enrolled, participants must meet all the inclusion criteria (Section 7.2.1) and none of the exclusion criteria (Section 7.2.2).

Enrolment will be based on the number of participants prescribed odevixibat and their willingness to participate in the registry-based study, but the goal will be to enroll approximately 30 to 45 participants with ALGS.

7.2.4 Study Duration

The duration of the registry-based study is approximately 5 years. Participants will be followed for ≥ 2 years. Enrolment will close 3 years after the start of the study to ensure participants are followed for ≥ 2 years. Following enrolment, participants will continue to participate in the study until the time point of withdrawal of consent, for up to 180 days after last dose of odevixibat (in case of treatment discontinuation), death, the end of data collection, or the sponsor decides to discontinue the study.

Participant enrolment will start on the date that the investigational site has been activated.

7.2.5 Study Place

The registry-based study will be implemented in the United States.

7.2.6 Study Schedule

The schedule of assessments that will be collected during the registry-based study is summarized in Table 1. As this is an observational study designed to assess real-world data, these assessments are not mandated by this protocol. If some assessments included here are not routinely performed by the investigator, the corresponding sections in the eCRF do not need to be completed. No additional assessments or tests will be required for the purpose of this study.

PROTOCOL: FINAL (WITH AMENDMENT #3): 10 DECEMBER 2024

PAGE 24 OF 76

 Table 1
 Schedule of Assessments

Assessment/Procedure	Baseline Visit Day 1	Follow up Visit(s) (as per routine clinical practice) ^{a,b}
Clinic visit	X	X
Informed consent ^c	X	-
Inclusion/exclusion criteria	X	-
Demographics and baseline characteristics ^d	X	-
Weight and height	X	X
Prior surgical procedures related to ALGS	X	-
General medical or surgical history	X	-
Prior medications ^e	X	-
Concomitant medications ^f	X	X
Concomitant vitamin supplementation ^g	X	X
Treatment with odevixibat (dates of treatment, dose, and changes/discontinuation)	X	X
Planned Biliary diversion surgery / Liver transplantation ^h	X	X
Biliary diversion surgery cancellation / Liver transplantation removal from listing	-	X
Clinical symptoms ⁱ	X	X
Laboratory parameters ^j	X	X
Concomitant surgical procedures	X	X
AEs and Special Situations ^k	X	X
Fat-soluble vitamin deficiency questionnaire ¹	X	X
Death report	-	X
Study discontinuation	-	X ^b

AE=adverse event; ALP=alkaline phosphatase; ALT=alanine aminotransferase; ALGS=Alagille syndrome; AST=aspartate aminotransferase; GGT=gamma-glutamyl transferase; INR=international normalized ratio; UDCA=ursodeoxycholic acid.

^a Follow-up Visits are expected to occur at least every 6 months according to routine clinical care or more frequently, based on the investigator's judgement. Investigators are encouraged to contact the participants (e.g., text-based reminders or phone calls to caregivers) to ensure follow-up visits are attended and to facilitate rescheduling, if necessary.

PROTOCOL: FINAL (WITH AMENDMENT #3): 10 DECEMBER 2024

PAGE 25 OF 76

- ^b End of study for participants: the last Follow-up Visit as per routine clinical practice before the planned end of data collection (Section 4), withdrawal of consent, lost-to follow up, or 180 days after treatment discontinuation, whichever comes first. In case of treatment discontinuation, the last Follow-up Visit is recommended to happen onsite approximately 180 days after last dose of odevixibat.
- ^c If the participant is < 18 years of age (or the legal age of consent in the jurisdiction in which the study is taking place), assent and parent or legally authorized representative consent will also be required. Participants who turn 18 years of age (or legal age per country) while participating in the study will be required to provide consent for themselves.
- ^d Including age, sex, date of birth (MM/YYYY), and date of ALGS diagnosis
- ^e Prior medications refer only to medications related to the treatment of ALGS, including but not limited to rifampicin, UDCA and/or other IBAT inhibitors. Treatments used up to 9 months prior to the first odevixibat dose are to be collected (including the dose). If prior medications are discontinued, the date of discontinuation is to be provided. If the prior medication involves other IBAT inhibitors, any adverse events leading to their discontinuation will be documented, including their resolution.
- f Concomitant medications include ALGS and non-ALGS oriented treatments, including but not limited to rifampicin and/or UDCA.
- g Type and dose of to be collected.
- ^h Planned date and indication are to be collected.
- ¹ Includes pruritus and sleep disturbance, if (semi-) objective scoring data are available. For non-naïve participants, the most recent values prior to the first odevixibat dose are to be collected.
- ^j Laboratory parameters include-AST, ALT, ALP, total bilirubin, direct bilirubin, GGT, INR, albumin, creatinine, sodium, platelet count, and serum bile acid levels reported since the prior data collection. At the Baseline visit, historical (the most recent values in the last 9 months prior to the first odevixibat dose) values are also to be provided if available.
- ^k AEs collection begins once the informed consent has been signed and will end 180 days after the last odevixibat dose (unless consent was withdrawn). Special Situations include pregnancy or breastfeeding status and overdose, off-label use, misuse, abuse, occupational exposure, medication error, and lack of effectiveness (Section 9.1.3).
- ¹ The fat-soluble vitamin deficiency questionnaire will be included in the eCRF and completed by the investigator (Section 7.6.1).

PAGE 26 OF 76

7.2.7 *Study Visit(s)*

Visits will be done in accordance with routine clinical practice (Follow-up Visits are expected to occur at least every 6 months or more frequently, based on the investigator's judgement). Investigators are encouraged to contact the participants (e.g., text-based reminders or phone calls to caregivers) to ensure follow-up visits are attended and to facilitate rescheduling, if necessary.

The registry-based study will assess data collected at the Baseline Visit and Follow-up Visits.

The End of Study for participants will be the last Follow-up Visit as per routine clinical practice performed before the planned end of data collection (approximately 5 years after the start of data collection, see Section 4), withdrawal of consent, lost-to follow up, or 180 days after treatment discontinuation, whichever comes first.

7.2.7.1 *Baseline*

Investigators at participating sites will identify participants who fulfil the inclusion and none of the exclusion criteria. Signed informed consent should be obtained prior to enrolment based on local regulations, and once inclusion and exclusion criteria have been satisfied. If the participant is < 18 years old (or the legal age of consent in the jurisdiction in which the study is taking place), assent and parent or legally authorized representative consent will also be required.

For this registry-based study, the following variables will be captured from Baseline Visit records as available:

- Age, sex, weight, height, ALGS genetic variant, date of birth (MM/YYYY), and date
 of ALGS diagnosis
- General medical or surgical history
- Prior surgical procedures related to ALGS, including but not limited to prior biliary diversion surgery (date and type of surgery) and liver transplantation (date and donor information)
- Prior medications
 - Prior medications refer only to medications related to the treatment of ALGS, including but not limited to rifampicin, UDCA, and/or other IBAT inhibitors, taken up to 9 months prior to the first odevixibat dose
- Concomitant medications
 - Concomitant medications include ALGS and non-ALGS oriented treatments, including but not limited to rifampicin and UDCA
- Concomitant vitamin supplementation
- Odevixibat treatment dose and start date
- Clinical symptoms: pruritus and sleep disturbance, if (semi-) objective scoring data are available. For non-naïve participants: most recent values prior to the first odevixibat dose are to be collected.
- Planned biliary diversion surgery (planned date and indication)
- Listing for liver transplantation (planned date and indication)
- Laboratory parameters, including alanine aminotransferase (ALT), aspartate aminotransferase (AST), alkaline phosphatase (ALP), total bilirubin, direct bilirubin, gamma-glutamyl transferase (GGT), international normalized ratio (INR), albumin, creatinine, sodium, platelet count, serum bile acid levels, and FSV levels. Historical

PAGE 27 OF 76

values (the most recent values in the last 9 months prior to the first odevixibat dose) are also to be provided at baseline if available.

- FSV deficiency questionnaire
- Pregnancy or breastfeeding status

7.2.7.2 $Follow-up\ Visit(s)$

The participants will attend a clinic visit and assessments will be performed according to routine clinical care. For this registry-based study, the following variables will be captured from medical records as available:

Odevixibat and Concomitant Medications and Surgery Data Collection:

- Odevixibat dose (if changed/discontinued, provide date and reason)
- Concomitant medication (ALGS and non-ALGS oriented treatments, including but not limited to rifampicin, UDCA)
- Concomitant vitamin supplementation
- Concomitant surgical procedures (including but not limited to biliary diversion surgery (date, indication, and type of surgery) and liver transplantation (date and donor information))

Periodic Safety Data Collection:

- Adverse events (including suspected hepatotoxicity requiring interruption of odevixibat treatment and bleeding events) and Special Situation
- Weight and height
- Fat-soluble vitamins levels and FSV deficiency questionnaire
- Death (date and cause)

Periodic Effectiveness Data Collection:

- Laboratory parameters, including AST, ALT, ALP, total bilirubin, direct bilirubin, GGT, INR, albumin, creatinine, sodium, platelet count, and serum bile acid levels reported since the prior data collection
- Planned Biliary diversion surgery (planned date and indication)
- Listing for liver transplantation (planned date and indication)
- Cancellation of planned biliary diversion surgery and reason for cancellation
- Removal from listing for liver transplantation and reason for removal from the list
- Clinical symptoms: pruritus and sleep disturbance, if (semi-) objective scoring data are available

